clustering within sites and will include the same covariates as for the primary analysis. The remission rate for non-responders who proceed to Phase II will be summarized separately depending on the treatment patients received during Phase I and Phase II. The 95% confidence interval for the rates will be provided.

12.3 Statistical Analyses: Aim 2

To evaluate the ability of biomarkers and phenotypic characteristics to predict response to therapeutic intervention, multivariable logistic regression analysis will be conducted with histological evaluation of remission/no remission as the dependent variable and biomarker levels as the independent variables. Multicollinearity of the independent variables will be assessed. The area under the receiver operating characteristic curve (AUROC) will be estimated along with 95% confidence interval. This analysis will be conducted based on the remission status at the end of Phase I. It will be repeated at the end of Phase II by including those patients who also responded to SGC.

A sample size of 292 total patients will provide at least 80% power to detect an AUROC of 0.60. This calculation is based on the assumption that 161 patients (66 1FED, 95 4FED) will be in remission at the end of Phase I (and therefore not move on to phase II) and 131 patients will not be in remission (with an estimated 10% dropping out and not continuing on to Phase II).

Additionally, a correlation analysis between PEES scores and biomarkers will be performed. Spearman's correlation coefficient and its confidence intervals will be computed to further assess predictive utility for the biomarkers of interest.

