4 STUDY PARTICIPANTS

4.1 Number of Participants

A total of 292 participants between the ages of 6-17 years were to be enrolled. Because of unexpectedly slow

enrollment, the actual number of participants will be around 50 total. The DMCC at the University of South Florida Health Informatics Institute will serve as the central data management center, with CCHMC serving as the primary site and the central IRB. Additional sites include: Children's Hospital of Colorado, Riley Hospital for Children, Children's Hospital of Philadelphia, University of California at San Diego/Rady Children's Hospital, Northwestern University/Lurie Children's Hospital, Tufts Medical Center, Mt. Sinai Kravis Children's Hospital, Arkansas Children's Hospital, and the University of North Carolina.

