 - Percent of participants who achieve histologic remission (<15 peak eosinophils/HPF) post therapy assessed after the end of the 3 months
 - Division of patients into complete (all peak eosinophils ≤1/HPF) or partial (the worse of 3 scores is from 2 to 14) remission, and non-remission (at least one > 14/HPF)
 - Histology Scoring system
 - Endoscopic scoring system (EREFS)
- Biomarkers pre- and post-treatment
 - Assessment of Eosinophil Diagnostic Panel EoE Score
- Clinical parameters and biomarkers to predict responsiveness to diet and SGC therapy

- Correlation of clinical characteristics to response to therapy
- Assessment of predictive value of skin prick and patch allergy skin testing
- Correlation between presence of positive milk component allergy testing to response to 1FED
- Predictive biomarker-analysis of EoE transcriptome from EDP analysis on baseline biopsies in correlation to response to treatment.

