5.2.1.1 Secondary End-Point Analysis: Biomarkers

In this sub-aim, we hypothesize that molecular biomarkers will change (improve) with each treatment phase, at least in part. Furthermore, we hypothesize that biomarkers may reveal (a) novel insight into therapeutic resistance and/or relapse; (b) reveal patient sub-groups not identified by histology; and (c) ultimately prove to be readily usable biomarkers in clinical settings and possess personalized medicine value. We will focus on molecular profiling of esophageal genes with the Eosinophil Diagnostic Panel (EDP), a set of 94 mRNA transcripts that have been established to differentiate EoE from controls (e.g. GERD and normal individuals), and to identify exposure and transcriptional signaling to SGCs²⁸. Essentially, the associated EDP algorithm renders the raw Ct values of each embedded gene after real-time PCR in a way that the upregulated genes and down-regulated genes are summed up individually. A quantitative “EoE score” is derived from the ΔCt (normalized to GAPDH) summation to reflect disease severity and for statistical analysis. Utilizing different gene sets, EDP is also able to predict steroid exposure and remission status based on the same algorithm²⁸. In this case, the EoE score will be calculated at baseline endoscopy and in the post-treatment biopsies to assess change with treatment.

The change in “EoE score” will be analyzed between responders and non-responders based on histology assessment (<15 eosinophils/HPF) at the end of Phase I via an ANOVA model, after proper transformation of the score, e.g. logarithmic if needed. If normality assumption is seriously violated, a non-parametric method of Wilcoxon test will be applied.

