5.2.2 AIM 2: Clinical Parameters & Biomarkers That Predict Therapeutic Response

5.2.2.1 Predictive Biomarker-Analysis Of EoE Transcriptome

In this sub-aim, we aim to identify biomarkers that may predict responsiveness to any or all of the treatment

interventions associated with this trial. As such, in this sub-aim, we will perform the EDP analysis on baseline biopsies, focused on identifying transcript levels that differentiate patients that respond to each of the interventions.

Baseline esophageal gene expression was compared between responders and non-responder patients by statistically screening two cohorts. A list of genes with $p < 0.05$ (or $FDR < 0.05$), fold change > 2.0 will be identified.

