- (2) Remission rates will be compared between the two treatment groups using the generalized linear mixed effects model with the logit link (for binary outcome) that accounts for the clustering within sites. Important covariates will be analyzed in this model including gender, race, PPI use, atopy, age, and anthropomorphic features. Treatment group comparisons for secondary endpoints will be performed using the generalized linear mixed effects model using the link that is appropriate for the endpoint (i.e. logit for binary, log for Poisson count, identity for continuous). These models will account for the clustering within sites and will include the same covariates as for the primary analysis.
- (3) The remission rate for non-responders who proceed to Phase II will be summarized separately depending on the treatment patients received during Phase I and Phase II. The 95% confidence interval for the rates will also be provided.

6.2 Statistical Analyses: Aim 2

To evaluate the ability of biomarkers and phenotypic characteristics to predict response to therapeutic intervention, multivariable logistic regression analysis may be conducted with histological evaluation of remission/no remission as the dependent variable and biomarker levels as the independent variables. Multicollinearity of the independent variables will be assessed. The area under the receiver operating characteristic curve (AUROC) will be estimated along with 95% confidence interval. This analysis will be conducted based on the remission status at the end of Phase I. It may also be repeated at the end of Phase II by including those patients who also responded to SGC.

Additionally, a correlation analysis between PEES scores and biomarkers will be performed. Spearman's correlation coefficient and its confidence intervals will be computed to further assess predictive utility for the biomarkers of interest.

Missing data will be handled in the following manner. For the primary efficacy measure of PEES, each patient is expected to complete the questionnaire; even if the patient terminates participation early (dropout) for any reason. The total PEES score is the average of 20 item scores, as long as there are at least 10 item response non-missing, as described previously. No imputation of missing total PEES will be performed. The early dropout reasons will be recorded, and rates will be assessed between treatment groups for potential patterns.

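### SAP 6.2's optional multivariable AUROC has no internal validation or predictor limit, and SAP 5.2.2.1 lets genes be listed on unadjusted p-values

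*SAP*

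**What the plan says.** SAP 6.2 states that "multivariable logistic regression analysis may be conducted with histological evaluation of remission/no remission as the dependent variable", with biomarker levels as the predictors, and then that "The area under the receiver operating characteristic curve (AUROC) will be estimated along with 95% confidence interval". The only model check it names is for multicollinearity. It gives no list or maximum number of predictors, no cross-validation, bootstrap or hold-out sample, and no method for the interval. SAP 5.2 lists the prediction work as separate strands: clinical characteristics ("Correlation of clinical characteristics to response to therapy"), skin tests, milk components and the EDP transcriptome.

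Protocol 12.3 planned the same analysis for a much larger trial: "A sample size of 292 total patients will provide at least 80% power to detect an AUROC of 0.60", assuming 161 patients in remission and 131 not. SAP 4.1 now expects that "the actual number of participants will be around 50 total", and the power statement is not carried over.

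For genes, SAP 5.2.2.1 describes an analysis "focused on identifying transcript levels that differentiate patients that respond to each of the interventions". Its rule is: "A list of genes with $p < 0.05$ (or $FDR < 0.05$), fold change > 2.0 will be identified". SAP 5.2.1.1 describes the panel as "a set of 94 mRNA transcripts".

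Protocol 6.5.2.4 reports 15 genes, found by raw p below 0.05 and fold change above 2.0, that had not passed FDR correction. It expects a replication cohort to give enough power to pass that filter, and commits to applying multiplicity-correction methods, with West-Young and Bonferroni as examples.

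**The concern.** A logistic model chooses its coefficients to separate the patients it is fitted to, so its AUROC in those same patients is too high, and more so with more predictors and fewer patients. The usual interval treats the fitted score as if it had been fixed in advance, so it sits around the inflated value. With no stated validation, the in-sample figure is the natural default, and a result at or above the protocol's target of 0.60 could come from markers that predict nothing.

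The gene rule has a related weakness. Its two thresholds are alternatives, so the raw p-value with the fold-change filter is enough. That is the rule behind the protocol's 15 genes that had not passed FDR. Protocol 6.5.2.4 wants such markers to help direct patients to diet or steroid, so a false lead would matter.

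**Working it through.** **1. The protocol's own figure.** Inputs from Protocol 12.3: AUROC 0.60 against 0.50, with m = 161 and n = 131. Alpha is 0.05, taken as two-sided (sidedness is not stated).

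- Null SE = √[(m+n+1)/(12mn)] = √[293/(12×161×131)] = 0.0340.
- Hanley-McNeil SE at A = 0.60: Q₁ = A/(2−A) = 0.4286 and Q₂ = 2A²/(1+A) = 0.45. SE = √{[0.24 + 160×0.0686 + 130×0.09]/(161×131)} = 0.0330.
- Power = Φ[(0.10 − 1.96×0.0340)/0.0330] = Φ(1.01) = 84%. The claim of at least 80% is reproduced.

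**2. The same at about 50.** The protocol's remission share is 161/292 = 55%, and 0.55 × 50 ≈ 28, so the assumed split is 28/22. The null SE is √[51/(12×616)] = 0.0831 and the Hanley-McNeil SE is 0.0804. Power = Φ[(0.10 − 0.1628)/0.0804] = Φ(−0.78) = 22%. Power of 80% would need a true AUROC of about 0.725.

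**3. In-sample AUROC on pure noise.** Each simulated dataset has independent standard normal markers unrelated to remission (true AUROC 0.50) and an unpenalised logistic fit. The AUROC is computed in the same patients, with a 95% CI by DeLong or Hanley-McNeil. There were 4,000 datasets per setting at 28/22 and 1,000 at 161/131. The last column is stratified 5-fold cross-validation repeated 10 times, on 1,600 noise datasets per setting.

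| Markers | Mean AUROC, 28/22 | CI wholly above 0.50, 28/22 | Mean AUROC, 161/131 | CI wholly above 0.50, 161/131 | Cross-validated mean, 28/22 |
|---|---|---|---|---|---|
| 1 | 0.565 | 6–7% | 0.526 | 5% | 0.50 |
| 2 | 0.602 | 17–19% | 0.541 | 13–14% | 0.50 |
| 3 | 0.630 | 31–34% | 0.552 | 28% | 0.50 |
| 5 | 0.676 | 61–65% | 0.571 | 58–59% | 0.49 |

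Separate runs gave the same means to within 0.01. Their exclusion shares were 15–19%, 30–33% and 59–62% for two, three and five markers at 28/22, and 14–16%, 26–28% and 54–59% at 161/131. Splits of 23/27 or 33/17 move the means by at most 0.01.

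**4. Screening first.** If the best two of 94 null transcripts are picked and then modelled in the same 50 patients, the mean in-sample AUROC is 0.77, and the CI excluded 0.50 in all 400 runs. The SAP does not say that listed genes feed the model; this shows why any screening has to sit inside the validation.

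**5. Genes.** With 94 null transcripts, raw p below 0.05 alone is expected to pass 94 × 0.05 = 4.7. The fold-change filter (log2 difference above 1) cuts this by an amount that depends on the log2 SD, which the documents do not give. At 28/22 the SE of a difference is SD × √(1/28 + 1/22) = 0.285 SD.

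- SD 1: a difference of 1 is 3.5 SEs. The filter removes nearly everything, leaving 0.04 expected false genes.
- SD 2: a difference of 1 is 1.75 SEs. The filter removes almost nothing, leaving 4.5.
- Intermediate SDs of 1.25 and 1.5 give 0.5 and 1.8.
- Within one diet arm (assumed 11/14 or 16/9) the range over the same SDs is 1.2 to 4.7.
- FDR below 0.05 plus the fold-change filter gives at most 0.07 throughout.

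**The case against.** The strongest reply is that the model is optional, its predictor count is unknown, and SAP 6.2 requires an interval. With two noise markers about four intervals in five still include 0.50, so most readers would see an inconclusive result. The EDP can be reduced to one EoE score, and Protocol 6.5.2.3 plans principal components for the component data, so few predictors may enter. This stands in part. With one prespecified marker the problem is negligible, and serious inflation begins at about three. But neither data reduction nor a multicollinearity check is validation, and the text describes a multivariable model.

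Several stronger readings are tempting and are not supported:

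- *Low enrolment causes the false positives.* The false-exclusion rate is similar at 161/131. The smaller sample mainly enlarges the point estimate.
- *The SAP says it will report the in-sample AUROC.* It does not. That is inferred from the absence of any other method.
- *All nine clinical items of Protocol 6.5.2.1 will enter together.* Neither document says so. Nine independent noise predictors would average 0.74, but height, weight and BMI Z-score overlap.
- *The SAP widens the gene screen or revokes the protocol's correction.* Protocol 6.5.2.4 already covers each intervention. Its firm commitment gives West-Young and Bonferroni as examples, in text about fluticasone response, with FDR as a filter that genes are expected to pass. The SAP makes adjustment optional within its own rule; it does not withdraw the commitment.
- *Most listed genes would be false.* The expected number runs from near zero to nearly five, depending on an unknown SD, and does not show that the protocol's 15 genes were chance findings.

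**Conclusion.** The point holds as a cheap improvement. If the ordinary in-sample AUROC is reported with two or more markers, it overstates prediction: about 0.60 on average from two noise markers and 0.68 from five, with the CI wrongly excluding 0.50 in about 17–19% and 60% of datasets. Real prediction at the protocol's target of 0.60 would be detected only about 22% of the time with one marker, so a reported value in the 0.60s would be hard to tell from noise. These figures assume a 28/22 split, independent normal markers and in-sample reporting.

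The gene-list point rests on the text: an unadjusted threshold is allowed as an alternative to FDR, while the protocol plans correction and reports that a list found by the unadjusted rule had not passed FDR. Its numerical size cannot be fixed from the documents.

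**What to change.** Amend the SAP before database lock.

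1. **SAP 6.2, estimate.** Report a repeated cross-validated AUROC as the main figure, with any screening, principal components or imputation redone inside each fold. Take the 95% CI from a resampling method that reruns the whole procedure, for example a patient bootstrap that keeps copies of one patient in one fold. With one or two prespecified predictors, an optimism-corrected bootstrap is a lesser alternative; on noise it still leaves about 0.53–0.54 with two. Ridge penalisation alone is not a substitute: the in-sample AUROC stayed at 0.60 and 0.67 with two and five noise markers.
2. **SAP 6.2, predictors.** Prespecify a small number in proportion to the smaller outcome class. One per 10 patients, for instance, allows two if that class is 22 and one if it is 17. The cap does not replace validation, since two noise markers already average 0.60 in-sample.
3. **SAP 6.2, status.** Label Aim 2 prediction exploratory, as the SAP already does for tests of treatment heterogeneity.
4. **SAP 5.2.2.1.** Require a multiplicity-adjusted criterion (FDR below 0.05, or a method named in Protocol 6.5.2.4) together with fold change above 2.0 for the reported list. Show raw p-values only descriptively.

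The cost is SAP wording and modest computing. AUROCs will be lower and the gene list may be short or empty. Intervals will be wide: in a two-predictor check of the patient bootstrap at 28/22 the mean width was 0.49, 0.41 and 0.31 at true out-of-sample AUROCs of 0.50, 0.68 and 0.79. That interval was conservative (coverage 99%, 98% and 96%) and lay wholly above 0.50 in 1%, 36% and 82% of datasets. It was not tested with screening or imputation inside the folds. Unless prediction is strong, Aim 2 may say little at about 50 patients, and the report should state that.

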9 PARTICIPANT WITHDRAWAL CRITERIA

An intent to treat approach will be used. All data acquired prior to termination for the reasons outlined below will be included in the primary analysis unless patient withdraws consent. Every effort will be made to conduct

a final study visit with the participant and participants will be followed clinically until, if applicable, all adverse events resolve.

- Withdrawal of consent
- Withdrawal by the participant
- Withdrawal by the investigator
- Intercurrent illness or event that precludes further visits to the study site or ability to evaluate disease (e.g.-mental status change, large pleural effusion).
- Participants will be discontinued from the study if they are unable to comply with the dietary restrictions or develop severe complications from their EoE (e.g., esophageal strictures).

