9.1 Replacement Of Participants

Enrolled participants who start on the initial dietary protocol and prematurely discontinue/withdraw from the study will be replaced if they do not reach Week 12 of the study including the EGD. Additional participants will be enrolled in the same manner as all other participants. Participant numbers will not be re-used. Any enrolled participant will be included into any intent to treat analysis.

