6 STATISTICAL METHODS

6.1 Statistical Analyses: Aim 1

Demographic and patient characteristics will be summarized for the two treatment groups using mean \pm standard deviation or median [interquartile range] for continuous variables and frequency and percentages for categorical variables. Treatment comparisons will be performed using the two-sample t-test or Wilcoxon Rank sum test for continuous variables and the Fisher's Exact test for categorical variables. All tests will be conducted at $\alpha=0.05$, including the primary and secondary analyses.

There was going to be two sets of analysis populations in terms of efficacy assessment, the intent-to-treat and per protocol. However, since the total enrollment has been reduced to about 50, all patients randomized to Phase I of the study who have at least one clinical observation post randomization will be considered in intent-to-treat set. Only this set of population will be included in the statistical analyses. Originally, we plan to define patients who are at least 80% compliant to dietary assignment during Phase I, and who do not have any major protocol violations as in per protocol set. Now all analyses will be based on intent-to-treat population. Patients who do drop out of the trial before the end of Phase I will have their PEES done at the time of dropout. The primary endpoint is overall PEES score change from pre-treatment to the end of Phase I. If normality assumption is approximately valid, a linear mixed effect model will be applied to the primary efficacy variable,

account for site random effect, and other potentially important covariates, e.g. gender, race, and PPI use etc. Because of non-normal nature of the scores in previous research, a Wilcoxon rank sum test may be applied to compare between two treatment groups when normality is violated.

As a secondary endpoint analysis, remission rates (as defined by the percentage of participants achieving histologic remission (eosinophils less than 15/HPF) at the end of Phase I will be analyzed in the following 3 steps.

- (1) Remission rates will be computed along with their 95% CIs for each diet group separately;

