For all other secondary efficacy and demographic variables, missing data will not be imputed. However, if a participant's biomarker panel is partially missing, multiple imputation may be applied for missing markers in predictive modeling analyses.

Heterogeneity of treatment effect is referred to as the variability in the direction and magnitude of individual or subgroup treatment effects that are non-random. Descriptive heterogeneity of treatment effect analyses will first be carried out for subgroups by gender, by study site, and by age of subject. These analyses are included in the analysis plan above for primary and secondary efficacy analyses, where proper estimates of treatment effect will be extracted. Because of the small sample size in this study, any hypothesis testing of treatment heterogeneity is considered exploratory. P-values generated from multiple comparisons are not adjusted. The goal is to identify possible heterogeneity among subgroups for further confirmation. The interaction of demographic and baseline characteristics with treatment group effects may be tested in the generalized linear mixed effects models to assess heterogeneity.

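### The no-imputation rule implies that participants without an end-of-Phase-I biopsy leave the remission analysis, which conflicts with the plan's intent-to-treat statements

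*SAP*

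**What the plan says.** - **Endpoint.** SAP Section 6.1 analyses "remission rates (as defined by the percentage of participants achieving histologic remission (eosinophils less than 15/HPF) at the end of Phase I" as a secondary endpoint. It gives a rate with a 95% CI for each diet, and then: "Remission rates will be compared between the two treatment groups using the generalized linear mixed effects model with the logit link". The denominator is not stated.
- **Analysis set.** In SAP Section 6.1, "all patients randomized to Phase I of the study who have at least one clinical observation post randomization will be considered in intent-to-treat set", and "Now all analyses will be based on intent-to-treat population". The only condition is one observation after randomisation, which could be a phone visit. Protocol Section 9.1 is wider: "Any enrolled participant will be included into any intent to treat analysis".
- **Missing data.** SAP Section 6.2: "For all other secondary efficacy and demographic variables, missing data will not be imputed". The one exception is multiple imputation of partly missing biomarker panels in the predictive models. Dropout reasons are to be recorded and dropout rates compared by arm, but nothing in the remission analysis depends on the result.
- **Early leavers.** Protocol Section 7.5 and Table 1 schedule the end-of-Phase-I procedures, including biopsies at a standard-of-care endoscopy, for those who withdraw early, within a week of stopping the diet. Neither document says whether that biopsy serves as the end-of-Phase-I result.
- **Replacement.** Under Protocol Section 9.1, a participant who does not reach Week 12 with its endoscopy is replaced.

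**The concern.** With no imputation and no rule for a missing biopsy, a logistic model uses only participants who have a biopsy result. A child with a Week 2 call and no later endoscopy belongs to the intent-to-treat set but contributes nothing to the remission comparison.

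That would matter little if biopsies were missing at random. Protocol Section 9, however, lists among its grounds for discontinuation that a participant cannot keep the diet, or that participants "develop severe complications from their EoE (e.g., esophageal strictures"). Both are plausibly linked to the assigned diet and to the outcome. The trial is open-label and one arm removes four foods while the other removes one, so the two arms may lose biopsies at different rates and for different reasons. Replacing those who miss Week 12 then refills the biopsied group with completers.

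At stake are the two reported remission rates with their intervals and the 1FED versus 4FED remission comparison. With about 50 participants (SAP Section 4.1), a handful of children can change how that comparison reads.

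**Working it through.** **1. The plan's own figures.** Protocol Section 12.1 takes response rates of 45% and 65%, so P = 0.5 × 0.80 + 1.0 × 0.20 = 0.60. The Noether formula for the Wilcoxon test (two-sided 0.05 assumed, 80% power) gives N = (1.960 + 0.842)² / (12 × 0.25 × 0.10²) = 261.6, or 131 per arm. Then 131 / 0.90 = 145.6, so 146 per arm and 292 in total. These reproduce.

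Protocol Section 12.3 expects 66 and 95 remitters: 146 × 0.45 = 65.7 and 146 × 0.65 = 94.9, with sum 161 and 131 not in remission. This also reproduces. The planning count therefore applies 45% and 65% to everyone enrolled, with expected dropouts still in the denominator. A complete-case rule would not do that.

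**2. Size of the overstatement in one arm.** Let c be the remission rate among biopsied children, r the rate among those without a biopsy, and d the fraction without one. The all-randomised rate is c(1 − d) + rd, so the complete-case rate exceeds it by d(c − r). With c = 65% and d = 20% (assumed):

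| r | Overstatement (points) |
|---|---|
| 0% | 13.0 |
| 30% | 7.0 |
| 65% | 0 |
| 80% | −3.0 |

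The sign depends on whether those without a biopsy remit less often than the rest.

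**3. Effect on the difference.** Take all-randomised rates of 45% and 65%, and assume nobody without a biopsy is in remission (r = 0). The complete-case rate is then p / (1 − d). The documents give only a 10% overall dropout, so the arm-specific values are assumptions.

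| Missing, 1FED / 4FED | 1FED | 4FED | Difference (points; 20 if all counted) |
|---|---|---|---|
| 10% / 10% | 50.0% | 72.2% | 22.2 |
| 5% / 15% | 47.4% | 76.5% | 29.1 |
| 10% / 20% | 50.0% | 81.2% | 31.2 |
| 15% / 5% | 52.9% | 68.4% | 15.5 |

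**4. At the actual size.** Assume 25 per arm, with 25 × 0.45 ≈ 11 and 25 × 0.65 ≈ 16 remitters. Fisher's exact test stands in for the mixed model.

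| Missing, 1FED / 4FED | 1FED | 4FED | Difference (points) | p |
|---|---|---|---|---|
| All randomised counted | 11/25 = 44.0% | 16/25 = 64.0% | 20.0 | 0.26 |
| 1 / 4 | 11/24 = 45.8% | 16/21 = 76.2% | 30.4 | 0.066 |
| 1 / 5 | 11/24 = 45.8% | 16/20 = 80.0% | 34.2 | 0.030 |
| 3 / 3 | 11/22 = 50.0% | 16/22 = 72.7% | 22.7 | 0.22 |
| 4 / 1 | 11/21 = 52.4% | 16/24 = 66.7% | 14.3 | 0.37 |

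The remitters are the same in every row. Only the treatment of children without a biopsy changes.

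**The case against.** **The complete-case denominator is inferred.** The SAP speaks of a percentage of participants and bases everything on intent-to-treat, and Protocol Section 9 describes that approach as including data acquired before termination, which is compatible with analysing observed data. This stands in part: the denominator is unstated. But the fitted model has to do something with a missing outcome, and no imputation means omission.

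**A biopsy is planned for early leavers.** Protocol Section 7.5 schedules it, Section 9 promises every effort at a final visit, and Section 4.9 says endoscopies take place whether or not a child is in the study. This narrows the problem to leavers with no endoscopy. It does not close it, because Section 6.4 requires no endoscopy beyond standard of care.

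**Counting a missing biopsy as non-remission is itself an assumption.** If missingness is unrelated to remission, it lowers the rates and can shrink a true difference. This stands, and is why both results are needed.

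**At this size noise dominates.** With 25 per arm and rates near 50%, the standard error of the difference is √(2 × 0.25 / 25) = 14 points. That is correct. But the shift from 20.0 to 34.2 points is about one standard error, and the confidence interval does not reflect it.

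Three stronger readings are tempting and unsupported:

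- A reader might infer that those who discontinue are failures by the protocol's definition. Protocol Section 9 lists reasons for withdrawal only; non-response is defined solely by biopsy, at 15 or more eosinophils per HPF (Protocol Sections 6.5.1.2 and 6.7).
- A reader might infer that the rule favours 4FED. Nothing says more children will abandon 4FED, and severe complications could fall more on the diet expected to work less well.
- A reader might apply 45% and 65% to biopsied children and conclude that, at 5% and 15% missing, the 20-point difference shrinks to 12.5 (0.65 × 0.85 − 0.45 × 0.95). Protocol Section 12.3 applies those rates to all 146 per arm.

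**Conclusion.** The point holds as an inconsistency in the analysis plan. The no-imputation rule implies that remission is analysed only in participants with a biopsy result, against the SAP's statement that all analyses use the intent-to-treat set and against Protocol Section 9.1.

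Bias is conditional. Both rates are overstated if children without a biopsy remit less often than those with one; the withdrawal reasons make this plausible, not certain. The between-arm bias can go either way, according to which arm lacks more biopsies. In the illustration at 25 per arm, the difference ranges from 14 to 34 points and p from 0.37 to 0.03, against 20 points and 0.26 with all randomised counted. These figures rest on assumed missing counts and on no remission among those without a biopsy.

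The primary PEESS comparison is not affected. This is a correction that should be made to a secondary endpoint.

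**What to change.** In SAP Sections 6.1 and 6.2:

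1. State that a biopsy from the early-withdrawal visit counts as the end-of-Phase-I result.
2. Report remission by arm over all randomised participants, counting those with no such biopsy as not in remission. Say that this set is slightly wider than the SAP's intent-to-treat set, and that replaced participants stay in it.
3. Report the complete-case rate and comparison beside it, and call the comparison robust only if the two agree.
4. Tabulate missing biopsies and their reasons by arm.

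The cost is a few sentences and one table, using data already collected; the planned dropout summary supplies much of the table. The SAP says it is set before the database is finalised, so the rule belongs there.

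The downside is that children who leave for unrelated reasons count as non-remitters. That lowers the rates, by more than a trivial amount if many biopsies are missing, and can shrink the difference when missingness is uninformative. The complete-case result beside it shows how much depends on the choice.
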